#### 4.10.1 Extent of Exposure and Compliance to Study Treatment

Participants will receive placebo (QD) or BHV-4157 (140 mg QD followed by 140 mg BID) during the Randomization Phase. For the Extension Phase subjects will receive open label BHV-4157 (140 mg QD followed by 140 mg BID).

For the Randomization Phase, the extent of participant exposure (including missed dose days) will be quantified as the number of days on study drug (placebo or BHV-4157) and measured from the time the participant received the first dose until the time the participant received the last dose (i.e., total days on randomized study medication = last day of double-blind randomized study medication – day 1 of double blind randomized study medication + 1).

For the Extension Phase, the extent of participant exposure (including missed dose days) will be quantified as the number of days on study drug (open label BHV-4157) and measured from the time the participant received the first dose in the Extension Phase until the time the participant received the last dose (i.e., total days on open label medication = last day of open label study medication – day 1 of open label study medication + 1).

For combined exposure of BHV-4157 either the randomization and the extension phase, the extent of participant exposure (including missed dose days) will be quantified as the number of days on study drug (BHV-4157) and measured from the time the participant received the first dose BHV-4157 until the time the participant received the last dose of BHV-4157 regardless of phase (i.e., total days on randomized study medication = last day of BHV-4157 study medication – day 1 of BHV-4157 study medication + 1).

Extent of participant exposure for a given phase or overall for BHV4157 will also be calculated only including days where number of capsules taken was >0 (total days on study medication).

For the Randomization Phase, the number of participants on-treatment and their average daily dose (including minimum and maximum) will be summarized by 14-day intervals for the first 28 days and then by month (28-day intervals) as well as overall for the randomization phase. For participants on placebo the number of capsules will be summarized.

For the Randomization Phase, the extent of study medication exposure will also be summarized by a Kaplan-Meier plot presenting proportion of participants still on Randomization Phase study medication (including days of missed dose).

For the Extension Phase and the entire study, the number of subjects on-treatment and their average daily dose (including minimum and maximum) will be summarized by month (30-day intervals) for the as well as overall for the Extension Phase and the entire study (BHV-4157 exposure).

Additionally, percent (%) compliance will be calculated and summarized as follows:

- Randomization Phase % compliance = total days on study medication (i.e. number of days where number of capsules taken > 0) during the Randomization Phase / (last dose date in Randomization Phase– first dose date + 1) × 100
- Extension Phase % compliance = total days on BHV-4157 in Extension Phase / (last dose date first dose date in Extension Phase + 1) × 100
- Overall % compliance = total days on BHV-4157 during the study / [(last BHV-4157 dose date first BHV-4157 dose date + 1) (number of days with a dosing break in dosing between the Randomization and Extension Phases)]

Summaries on the Randomization Phase will be repeated for Treated subjects completing (or discontinuing) double-blind treatment prior to versus on or after start of COVID-19 pandemic crisis (March 13, 2020).

Study drug administration and compliance will be listed in participant data listings.

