Rationale	BHV-4157 is a new chemical entity 3rd-generation prodrug of the glutamate modulator, riluzole, which has been designed to bypass first-pass metabolism therein providing greater bioavailability, diminished PK variability, lower hepatic burden, lack of food effect, longer half-life and once daily dosing. Preclinical models suggest that riluzole, the active metabolite of BHV-4157, may protect from AD-related pathology and cognitive dysfunction.
Target Population	Male and females, age 50 to 85 years (inclusive at screening), diagnosed with Alzheimer's Disease (in accordance with NIA/Alzheimer's Association Guidelines) of mild to moderate severity including MMSE score 14-24 at the screening visit.
	Eligible participants should be receiving a stable dose of FDA-approved AD medication(s) (acetylcholinesterase inhibitors (AchEI) and/or memantine) for at least 3 months prior to screening and willing to remain on same dose(s) for trial duration. Those participants with contraindications or failed treatment with either AchEI and/or memantine will be eligible for inclusion.
Number of Participants	Approximately 336 participants will be randomly allocated using a 1:1 allocation to active treatment or placebo.
Drug Dosage & Treatment Duration	Titrated dose of BHV-4157 to 280 mg, or placebo, taken orally once daily. Duration of double-blind treatment is approximately 48 weeks. There is also a screening period of up to 42 days; and a 4-week post-treatment observation period. Eligible subjects will have the opportunity to continue in a 48-week openlabel extension phase (once it is open for recruitment at their investigative site).
Objectives	Randomized Double-Blind Treatment Phase
	The co-primary objectives are to: evaluate the efficacy of BHV-4157 as measured by a) ADAS-Cog 11, and b) CDR-Sum of Boxes.
	The secondary objectives are to: (1) evaluate the efficacy of BHV-4157 as measured by: volumetric MRI (Quarc bilateral hippocampal volume)

Neuropsychiatric Inventory (NPI), ADCS-ADL, and Mini-Mental State Examination (MMSE). (2) evaluate the safety and tolerability of BHV-4157 as measured by mortality rates, serious adverse events, adverse events, clinical safety laboratories, physical examinations and significant ECG changes.

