6 STUDY DRUG

6.1 Study Medication

The double-blind phase medication will be presented as one of the following:

- BHV-4157, 1 or 2 capsules (size 1) of 140 mg each, depending on assigned dose, and
- 1 or 2 capsules of matching Placebo

The Open-Label Extension phase medication will be:

BHV-4157, 1 or 2 capsules (size 1) of 140 mg each

[figure not shown]
The study medication capsule should not be opened.

[figure not shown]
The study medication will be securely stored at the study site in accordance with the conditions specified on the label, separately from other drugs. The study medication may not be used for any purpose other than this study.

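### The compliance percentage counts any day with at least one capsule, so a participant prescribed two capsules a day who takes only one scores 100%

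*SAP*

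**What the plan says.** SAP 4.10.1 gives three compliance percentages. For the Randomization Phase the numerator is "total days on study medication (i.e. number of days where number of capsules taken > 0", and the divisor and scaling are "last dose date in Randomization Phase– first dose date + 1) × 100". The Extension Phase version begins "Extension Phase % compliance = total days on BHV-4157 in Extension Phase" and divides by the calendar span of extension dosing. The overall version is also days over days, with the break between phases taken out. The explicit more-than-zero rule reaches the Extension Phase and overall figures through an exposure definition in the same section, which applies to a given phase or overall: "only including days where number of capsules taken was >0 (total days on study medication". No formula contains a term for capsules prescribed.

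The regimen uses more than one capsule. Protocol 6.1 supplies active drug as "1 or 2 capsules (size 1) of 140 mg each, depending on assigned dose", with "1 or 2 capsules of matching Placebo". The protocol's study summary gives the target as "Titrated dose of BHV-4157 to 280 mg, or placebo, taken orally once daily", which is two capsules. Protocol 8.1.3 makes the week 2 escalation conditional on tolerability, and Protocol 11.4 recognises either 140 mg or 280 mg as a prescribed daily dose.

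SAP 4.10.1 also plans average daily dose with minimum and maximum by interval and overall (number of capsules for placebo), a Kaplan-Meier plot of time on study medication, and participant listings of drug administration and compliance.

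**The concern.** A statistic labelled compliance will be read as adherence to the assigned dose. This one measures something narrower: the share of days on which any dose was taken. Once the prescribed dose is two capsules, a day at half dose and a day at full dose both count as one, and the percentage cannot tell them apart.

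The figure matters for interpretation. The primary estimand (SAP 4.3.1.1) takes treatment as it was actually used and absorbs missed and modified doses. The supplemental on-treatment analysis of the co-primary endpoints (SAP 4.8.3) selects assessments by their distance from the last dose, not by the amount taken. Anyone reading either result, a null one especially, will want to know how much of the assigned dose participants took. The same percentage is also to be repeated for participants finishing before versus on or after the start of the COVID-19 pandemic, so the blind spot carries into that comparison.

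**Working it through.** The documents state no compliance value, so there is no figure to reproduce. The check applies the SAP formula to simple dosing patterns and compares it with a capsule count.

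**Inputs**
- Duration: 48 weeks = 336 days (Protocol study summary).
- Capsule strength 140 mg, target 280 mg, so two capsules a day after escalation (Protocol 6.1 and study summary).
- Escalation: at the week 2 call, if tolerated (Protocol 8.1.3). Assumed here as one capsule on days 1 to 14 and two from day 15. Titration lengths of 0 and 17 days are also shown, 17 being week 2 plus the 3-day window.

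**Formulas**
- SAP: 100 × (days with more than 0 capsules) / (last dose date − first dose date + 1).
- Capsule count: 100 × (capsules taken) / (capsules prescribed).

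**Prescribed total for a participant who escalates:** 14 × 1 + 322 × 2 = 658 capsules.

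**One capsule every day, two prescribed after titration**
- SAP: 336/336 = 100%.
- Capsule count: 336/658 = 51.1%.
- No titration period: 336/672 = 50.0%. Seventeen titration days: 17 + 319 × 2 = 655, and 336/655 = 51.3%. The SAP figure is 100% in each case.

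**Half dose on alternate days after titration**
- Taken: 14 + 161 × 1 + 161 × 2 = 497.
- SAP: 100%. Capsule count: 497/658 = 75.5%.

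**Whole days missed, about one in ten (34 of 336)**
- SAP: 302/336 = 89.9%.
- Capsule count: 67 capsules lost if one of the 34 days falls in titration (1 + 33 × 2), so 591/658 = 89.8%.
- Here the two measures agree.

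**Average daily dose of the one-capsule participant:** 140 mg, against 140 × 658/336 = 274.2 mg prescribed. A participant kept at one capsule because the first dose step was not tolerated, and who takes it every day, also averages 140 mg. The dose summary gives both the same value, and the SAP percentage gives both 100%. Capsules taken over capsules prescribed gives the first 51.1% and the second 336/336 = 100%.

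**The case against.** The strongest reply is that compliance is descriptive and that the same section already reports dose intensity. Average daily dose comes with minimum and maximum, by interval and overall, and drug administration is listed by participant. A half-dosing participant would pull down the minimum and be visible in the listing. Time after the last dose is covered by the Kaplan-Meier plot, and plasma concentrations are summarised by visit (SAP 4.9). Compliance defines no analysis population (SAP 3.1) and enters no primary, sensitivity or supplemental model (SAP 4.8.3).

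All of that stands, and it rules out several stronger readings. A reader might infer that under-dosing is hidden from the report; it is not, because the dose summaries and listings show it. A reader might infer that the percentage would look near-perfect whatever participants did; it would not, because wholly missed days between first and last dose stay in the denominator. A reader might infer that an efficacy result is biased; nothing in the plan connects compliance to one.

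It is also fair to say that one capsule a day can be the prescribed dose. For a participant who was not escalated, 100% is right, and a uniform denominator of 658 would wrongly score that participant 51%. This limits how the fix can be built.

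The reply does not remove the main point. The dose summaries are not set against what was prescribed, so they leave a non-escalator and a half-dosing participant looking alike. The percentage is the one planned output that carries the name of adherence, and it does not separate them either.

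**Conclusion.** The point holds for partial-dose days only. As written, the SAP formula reports 100% for a participant who is prescribed two capsules and takes one every day, when about 51% of the prescribed capsules were taken (50.0% to 51.3% across the titration lengths tried). This rests on a 336-day course, daily capsule counts being available as the more-than-zero rule presupposes, and the participant having actually been escalated.

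The 51% is an illustrative extreme for one participant. The documents give no indication of how often partial-dose days occur, so the effect on group compliance cannot be estimated. No p-value, estimate or analysis population changes. The consequence is a misleading adherence figure, which is worth correcting because it is cheap to correct and because the figure will be used to interpret the result.

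Separately, the protocol's study summary describes once-daily dosing while SAP 4.10.1 describes the escalated dose as 140 mg twice daily. These passages must be reconciled. Both imply two capsules a day, so the calculation above is unaffected.

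**What to change.** In SAP 4.10.1, define % compliance for each phase and overall as capsules taken divided by capsules prescribed to that participant over the dosing period, times 100. The prescribed count should follow the participant's own recorded regimen, so that anyone not escalated is judged against one capsule a day. Keep the present any-dose-day percentage as a second line under a label that says what it is. It remains useful because in a pooled capsule count extra capsules on one day can offset a missed day.

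The cost is SAP wording and one derived variable. The numerator uses the daily capsule counts that the current rule already requires. The denominator needs each participant's escalation status and date. The visible text does not show the field that holds these, and the protocol's dosing sections are partly redacted, so the team should confirm the source, for example the record of the week 2 call. The resulting figure may look less favourable than the present one.

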#### 4.10.2 Adverse Events

AEs will be coded using MedDRA and displayed in tables and listings by system organ class (SOC) and preferred term (PT).

Analyses of AEs will be performed for those events that are considered treatment-emergent (TEAE), where treatment-emergent is defined as events that first occurred or worsened on or after first dose of study medication. See section 4.4 for the detailed definition of "on-treatment" treatment-emergent AEs (TEAEs) and see section 4.3.7 for additional details when onset date is partial.

The number and percentage of participants with the following AEs will be summarized by treatment group and overall for the Randomization and Extension Phases, separately, as well as just overall for subjects after at least one dose of BHV-4157 in any phase.

- TEAEs
- TEAEs Related, Probably Related or Possibly Related to Treatment (An AE is considered to be related to study drug if the relationship is either definitely, probably or possibly related.)
- Treatment-emergent SAEs
- TEAEs leading to discontinuation of study treatment
- TEAEs by highest severity (mild, moderate, severe)
- TEAEs Related, Probably Related or Possibly Related to Treatment by highest severity (mild, moderate, severe)
- TEAEs indicating potential Interstitial Lung Disease (using Standardized MedDRA Queries (SMQ) Interstitial Lung Disease including Eosinphilic Pneumonia and Hypersensitivity Pneumonitis)

In the above tabulations, each participant will contribute only once for a given preferred term (i.e., the most related occurrence or the most severe occurrence) to each of the incidence rates in the descriptive analysis, regardless of the number of episodes. No formal hypothesis-testing analysis of AEs incidence rates will be performed.

All AEs occurring pre-treatment, during the Randomization and Open Label Extension Phases, and throughout the entire study will be listed. Additional listings will be provided including all deaths, SAEs, and AEs leading to withdrawal of study drug.

Listings will indicate whether subject was active during COVID-19 pandemic crisis and the date of first visit impacted.

#### 4.10.3 Laboratory Data

Clinical laboratory evaluations include:

- Hematology: hemoglobin, hematocrit, platelets, complete blood count with differential and absolute neutrophil count
- Serum Chemistry: sodium, potassium, chloride, calcium, ALT, AST, LDH, alkaline phosphatase, GGT, phosphorous, bicarbonate, CPK, total protein, albumin, direct bilirubin, indirect bilirubin, total bilirubin, glucose, creatinine, BUN, uric acid, total cholesterol, LDL, HDL, triglycerides
- Urinalysis: pH, specific gravity, protein, glucose, ketones, urobilinogen, bilirubin, blood

Clinical laboratory values will be expressed using conventional (US) and standard international (SI) units. In the event of repeat values within the same analysis visit, if any measurement has abnormal results, that measurement will be used for presentation in by-visit tables. If none of the measurements are abnormal, or all of them are abnormal, the worst measurement in the analysis

visit interval will be used for presentation in by-visit tables. All measurements will be presented in listings and considered for evaluation of potential drug- induced liver injury (DILI) or abnormalities.

Due to the COVID-19 pandemic crisis some sites might utilize local laboratories for some visits. These local laboratory values will be combined with the centralized laboratory values by normalizing them to the central laboratory using methods described in Chuang-Stein 1992

On-treatment laboratory abnormalities are those with an assessment date after the date/time of first dose of study drug and within 30 days after the last dose of study drug. For the Randomization Phase, treatment-emergent laboratory abnormalities will be assessed from the date of first dose of study drug until: 1) the first day of the Extension Phase or 2) if the subject did not continue into the Extension Phase, 30 days after the last dose of study drug. For the Extension Phase, treatment-emergent lab abnormalities will be assessed from the first dose during the Extension Phase until 30 days after the last dose of study drug. (See section 4.3)

The observed value and change from baseline will be summarized for each continuous laboratory parameter for the Randomization and Extension Phases, separately, in both conventional and SI units.

Clinical laboratory test results will be graded according to CTCAE version 5.0 if criteria for test available, otherwise according to DAIDS version 2.1 criteria, if available for test. The number and percent of participants with at least one on-treatment lab assessment by highest grade will be summarized for each treatment (regardless of baseline) for the Randomization and Extension Phases, separately as well as just overall for subjects after at least one dose of BHV-4157 in any phase. In addition, the shift from baseline to worst on-treatment lab (based on either normal limits or grading, where available) will be tabulated by visit and the overall minimum and maximum observed for treated subjects in the Randomization and Extension Phases, separately, as well as just overall for subjects after at least one dose of BHV-4157 in any phase. The shift tables will include only participants with a baseline assessment and at least one on-treatment assessment.

For the liver function tests, AST, ALT, Alk Phos, and BILI the shift from baseline will also be presented by visit and to the maximum observed abnormality for the Randomization Phase and Extension Phases, separately, as well as just overall for subjects after at least one dose of BHV-4157 in any phase. Baseline in the shift tables will be defined as per Section 4.2.8; the last available assessment on or before the first day of study treatment in that phase. Shift tables will only include treated participants with an assessment for the specific test of interest at baseline and on treatment. The following categories will be used to summarize the shift from baseline based on the upper limit of normal (ULN) range for ALT and AST:

- <=ULN
- >ULN to  $\leq$  3x ULN
- >3x ULN to  $\leq 5x$  ULN
- >5x ULN

The following categories will be used to summarize the shift from baseline based on the ULN range for alkaline phosphatase:

- <=ULN
- >ULN to  $\leq 1.5 \text{x}$  ULN
- >1.5x ULN to  $\leq$  2.5x ULN
- >2.5x ULN

For GGT, the following categories will be used to summarize the shift from baseline:

- <=ULN
- >ULN to  $\leq 2.5 \text{x}$  ULN
- >2.5x ULN

The following categories will be used to summarize the shift from baseline based on the ULN range for Total Bilirubin BILI:

- <=ULN
- >ULN to  $\leq 1.5$ x ULN
- >1.5x ULN to  $\leq$  2.0x ULN
- >2.0x ULN

An evaluation of drug-induced serious hepatotoxicity (eDISH) scatter plot will display the maximum TBL ratio of value to ULN on the y-axis versus the maximum ALT ratio of value to ULN on the x-axis, where the maxima is not necessarily concurrent, for treated subjects in the randomization phase and DB and OL BHV-4157 treated subjects. Both axes will be on the log10 scale. Ratios < 0.1 x ULN will be set to 0.1. Sample sizes in the legend will represent subjects with paired ratios. A horizontal reference line will be placed at 2 x ULN, and a vertical reference line will be placed at 3 x ULN. The lower left quadrant will be labeled "Normal Range", the upper left quadrant will be labeled "Hyperbilirubinemia", the lower right quadrant will be labeled "Possible Hy's Law Range."

All laboratory data will be presented in data listings. Additional listings will be presented for all abnormal laboratory values considered potentially clinically significant (Grade 3 or 4) for the Randomization and Extension Phases. Participants with a maximum value of ALT or AST >3x ULN or a maximum total bilirubin value >2x ULN observed at any point during the entire study will also be presented in a listing. Note that these abnormalities do not need to occur on concurrent visits.

The following summary for the Randomization Phase will be repeated for Treated subjects completing (or discontinuing) double-blind treatment prior to versus on or after start of COVID-19 pandemic crisis (March 13, 2020):

The number and percent of subjects with at least one on-treatment lab assessment by highest grade will be summarized for each treatment (regardless of baseline) for the Randomization Phase

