#### 4.10.9 Subjects Identified for Narratives

A safety narrative will be prepared for each subject who received at least one dose of troriluzole and experienced the following events (regardless of relationship to study drug) on-treatment with Troriluzole:

- All deaths on-treatment and post-treatment through the end of the study
- SAEs on-treatment, which includes up to 30 days after the last dose of study drug; SAEs that occur > 30 days (i.e., during the follow-up period) will be included per the clinical judgment of the Biohaven medical monitor
- All premature discontinuations of study drug due to AEs (either identified through "action taken" or "end of treatment status")
- The following on-treatment events of special interest:
  - Neutropenia based on laboratory results and defined as minimum absolute neutrophil count < 500 per mm3

  - LFT abnormalities:
    - $\circ \quad \text{ALT or AST} > 3x \text{ ULN}$
    - ALT or AST > 3x ULN, and serum total bilirubin > 2x ULN

Interstitial lung disease Standardized MedDRA Query (SMQ) including eosinophilic pneumonia and hypersensitivity pneumonitis

These select events are described in the current version (v3) of the Biohaven Safety Narrative Scope for BHV-4157 (troriluzole). Because select events may be subject to change, updates to the list of events or selection algorithms after database lock may be described in a Note to File (NTF) rather than amending the SAP.

A by-subject listing of safety narrative subject identifiers will be presented for all troriluzole treated subjects with the select events as described above.

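### The SAP's eDISH plot puts the Possible Hy's Law label on the isolated-ALT quadrant and leaves the quadrant where ALT and bilirubin are both raised without a label

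*SAP*

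**What the plan says.** SAP section 4.10.3 (Laboratory Data) describes an eDISH scatter plot for treated participants in the randomization phase and for those treated with BHV-4157 in the double-blind and open-label phases. It plots the "maximum TBL ratio of value to ULN on the y-axis" against "the maximum ALT ratio of value to ULN on the x-axis", and notes that the two maxima may come from different times. For the cut-points: "A horizontal reference line will be placed at 2 x ULN, and a vertical reference line will be placed at 3 x ULN".

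The quadrants are then named. "The lower left quadrant will be labeled 'Normal Range"; the upper left is called *Hyperbilirubinemia*; and "the lower right quadrant will be labeled 'Possible Hy's Law Range". No label is given for the upper right.

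SAP section 4.10.9 (Subjects Identified for Narratives) lists two liver triggers: ALT or AST above 3x ULN on its own and, as a separate entry, "ALT or AST > 3x ULN, and serum total bilirubin > 2x ULN".

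**The concern.** The Hy's Law label sits on a quadrant where, by the plot's own reference lines, bilirubin is not raised beyond 2x ULN. The quadrant where both ALT and bilirubin exceed their lines is left without a name. A programmer following section 4.10.3 literally would produce a figure whose annotation misdirects the reader: isolated ALT elevations would appear under a Hy's Law heading, and participants exceeding both thresholds would not be flagged.

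What is at stake is how one safety figure is read. That figure has some weight. The shift tables in section 4.10.3 take each liver test separately, and the liver listing there admits a participant on either a transaminase or a bilirubin criterion. The combined criterion in section 4.10.9 applies only to participants who received troriluzole. The eDISH plot is the planned display that pairs ALT with bilirubin and also includes placebo participants, so its labels affect how the arms are compared on that pairing.

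**Working it through.** No sample size, power or error rate is involved, so the check is logical: classify one point per quadrant using the SAP's own axes and lines, then compare the result with the SAP's labels and with its combined liver criterion.

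**Inputs**
- y-axis: maximum total bilirubin/ULN; "A horizontal reference line will be placed at 2 x ULN" (section 4.10.3).
- x-axis: maximum ALT/ULN; "a vertical reference line will be placed at 3 x ULN" (section 4.10.3).
- Labels given: lower left, upper left and lower right (section 4.10.3).
- Combined criterion: transaminase above 3x ULN together with total bilirubin above 2x ULN (section 4.10.9).

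**Rule.** A point is on the right if ALT/ULN > 3, otherwise on the left. It is in the upper half if bilirubin/ULN > 2, otherwise in the lower half.

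| ALT (x ULN) | Bilirubin (x ULN) | Quadrant | SAP label | Meets the combined criterion through ALT? |
|---|---|---|---|---|
| 1 | 1 | lower left | Normal Range | no |
| 1 | 3 | upper left | Hyperbilirubinemia | no |
| 5 | 1 | lower right | Possible Hy's Law Range | no |
| 5 | 3 | upper right | none | yes |

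**Reading the table.** The two left-hand labels fit the axes. The third does not: a participant at (5, 1) has a raised ALT only, yet falls under the Hy's Law label. A participant at (5, 3) exceeds both lines and meets the combined criterion of section 4.10.9, yet falls in the one quadrant with no name. No other section of the SAP or the protocol gives a different assignment of labels.

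**After the correction.** With the Hy's Law label on the upper right, the labelled region is ALT/ULN > 3 and bilirubin/ULN > 2, which matches the combined criterion in section 4.10.9 as far as ALT is concerned. The lower right then needs a name of its own.

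**The case against.** **This may be lost wording rather than a decision.** The sentence names three of four quadrants, has no conjunction before the last, and gets the first two right. That is what would remain if a lower-right label and the words introducing the upper right had dropped out. The loss could have occurred in drafting or in conversion of the PDF; the text shows no gap or redaction mark, so neither is established. This stands as a likely explanation and a reason to check the source. It does not make the instruction usable as it reads now.

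**The effect stops at annotation.** This stands in full. Axes and reference lines are correct, so every point is in its proper place and a participant with both values raised can be seen at upper right. No count or test is derived from the label. All laboratory data are listed, participants with high ALT, AST or bilirubin have a dedicated listing, shift tables cover each liver test, and narratives are written for troriluzole recipients who meet the liver triggers.

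**Stronger readings that the documents do not support.** A reader might infer any of the following.
- *The plot would contradict the narrative list.* It would not: section 4.10.9 also triggers a narrative for ALT or AST above 3x ULN alone, so troriluzole recipients in either right-hand quadrant meet a trigger on the same values. That section does not use the term Hy's Law.
- *Liver injury is the drug's main named risk.* Protocol sections 1.7.1.3 to 1.7.1.5 treat liver tests, neutropenia and interstitial lung disease in parallel.
- *The number mislabelled can be forecast.* The protocol's 8% for riluzole, applied to 168 active participants, gives 0.08 x 168 = 13.4. But that rate comes from ALS patients on riluzole, the protocol reports no ALT or AST above 3x ULN in studies 102, 103 or 201 of BHV-4157, and the sum assumes that none of these participants has raised bilirubin. It also leaves out placebo and open-label participants, who are plotted too.
- *The plot must also show AST.* An ALT-only plot is a legitimate choice, and AST is covered by the listing, shift tables and narratives.

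**Conclusion.** The point holds as a labelling error of minor severity. Taken literally, section 4.10.3 names the isolated-ALT quadrant as the Hy's Law range and leaves the quadrant with both elevations unnamed. This follows from the SAP's own axes and lines and needs no outside definition beyond the combination that section 4.10.9 already lists separately.

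Participants in the upper right should be called possible candidates and no more: the maxima need not be concurrent, so a point there does not show that ALT and bilirubin were raised together. No number of affected participants is claimed, and no efficacy result or other safety output changes. The conclusion assumes that the sentence as it reads is what the SAP contains. If the source file turns out to carry the missing words with the correct assignment, the point falls away.

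**What to change.** First check the eDISH sentence in section 4.10.3 against the SAP source file. If it stands as it reads now, reword it so that all four quadrants are named: keep the two left-hand labels, assign *Possible Hy's Law Range* to the upper right (ALT above 3x ULN and total bilirubin above 2x ULN), and give the lower right its own label for isolated ALT elevation (ALT above 3x ULN, total bilirubin not above 2x ULN). Carry the same labels into the figure specification.

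The cost is one sentence in the SAP and the text on one plot. No new data are needed, and nothing else in the safety analysis has to change.
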